All patients admitted to the medical critical care unit side 1 (MCC1) or side 2 (MCC2) will be provided a “Notice of Research.” At any time, refusal or withdrawal from the study can be requested by the patient, patient advocate, or provider.

Patients that meet inclusion criteria for the study will receive either hydrocortisone 50 mg IV Q6h alone or a combination of hydrocortisone 50 mg IV Q6h plus fludrocortisone 50 mcg PO/PER FT daily. Fludrocortisone must be initiated and administered within 24 hours after the first administered dose of hydrocortisone. Because fludrocortisone is only available as a 100 mcg tablet, the nurse at the bedside will split the tablet into two as to provide a 50 mcg dose. This is standard of practice currently when fludrocortisone is utilized in our institution.

Steroid therapy assignments will be randomized based on patient location. For three consecutive months starting in October 2018, all patients in MCC1 will receive hydrocortisone alone and all patients admitted to MCC2 will receive hydrocortisone plus fludrocortisone. Then, in the following three consecutive months, this will be flipped and MCC1 will receive hydrocortisone plus fludrocortisone while MCC2 will receive hydrocortisone alone. This change in group assignments will occur to account for the difference in number of beds between MCC1 and MCC2, and to minimize the potential differences in patient acuity by location.

Initiation of hydrocortisone for inclusion in the study will be determined solely by provider discretion as the standard of care for septic shock patients. Once hydrocortisone is initiated, fludrocortisone will be initiated within 24 hours for patients on the qualifying side of the unit, unless any of the previously stated exclusion criteria are present. Because these interventions are currently utilized and considered standard of care in the MCC, data collection will be performed retrospectively by generating a list of patients in the MCC receiving hydrocortisone therapy.

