Frequency and percentage statistics will be used to analyze categorical demographic, predictor, confounding, and outcome variables of interest for the sample. Descriptive statistics will be used to describe the sample characteristics associated with continuous variables. The assumption of normality of continuous distributions will be assessed using skewness and kurtosis statistics. If either statistic is above an absolute value of 2.0, then the distribution will be assumed to be non-normal. Homogeneity of variance between independent groups will be tested using Levene's Test for Equality of Variances. When both statistical assumptions are met, independent samples t-tests will be used to compare the treatment groups on continuous outcomes. Means and standard deviations will be reported and interpreted for these analyses. Mann-Whitney U tests will be used for comparisons when statistical assumptions are violated. Medians and interquartile ranges will be presented and analyzed for non-parametric comparisons. Chi-square tests will be used to test for significant associations between the treatment groups and categorical outcomes. Relative risk with 95% confidence intervals will be reported for significant categorical associations. Multiple regression analysis will be performed with time to resolution of shock as the outcome. Linearity, normality, homoscedasticity, multicollinearity, and autocorrelation assumptions for the regression analysis will be performed. Unstandardized beta coefficients, standard errors of the coefficients, and standardized beta coefficients will be reported and interpreted, along with the change in shared variance (R^2) and respective F-tests. All analyses will be conducted using SPSS Version 22 (Armonk, NY: IBM Corporation) and statistical significance will be assumed at an alpha value of 0.05.

A priori subanalysis will be performed on the following subset of patients: documented history of heart failure and documented chronic kidney disease stage III and IV requiring renal replacement therapy at baseline.

Critical Analysis/Limitations:

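### A failed Levene test alone sends data that pass the normality check to Mann-Whitney and medians, which does not correct for unequal variances and leaves the difference in means used to size the trial

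*Combined protocol and SAP*

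**What the plan says.** The rule is in Statistical Analysis, Statistical methods. Two checks come first.

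- Normality, by skewness and kurtosis: "If either statistic is above an absolute value of 2.0, then the distribution will be assumed to be non-normal".
- Equal variance: "Homogeneity of variance between independent groups will be tested using Levene's Test for Equality of Variances".

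The test then follows from the checks.

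- Both pass: "When both statistical assumptions are met, independent samples t-tests will be used to compare the treatment groups on continuous outcomes". For this branch, "Means and standard deviations will be reported and interpreted for these analyses".
- Otherwise: "Mann-Whitney U tests will be used for comparisons when statistical assumptions are violated". For this branch, "Medians and interquartile ranges will be presented and analyzed for non-parametric comparisons".

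No unequal-variance t-test is named anywhere. The rule covers every continuous outcome, including the primary endpoint (time to resolution of shock), both lengths of stay and duration of steroid therapy.

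Statistical Power sizes the trial on a difference in means of 96 vs 72 h, with SD 36 h in each group, two-sided alpha 0.05 and 1:1 allocation, giving 39 per group. The Protocol section assigns treatment by unit side and swaps the sides after three months, in part "to account for the difference in number of beds between MCC1 and MCC2".

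**The concern.** The rule gives two different problems the same remedy. A rank test is a common choice when data look non-normal. It is not a remedy for unequal variances: when spreads differ, Mann-Whitney is not a valid test of equal means, nor in general of equal medians. The test built for that situation is the Welch t-test, which keeps the comparison of means.

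The switch also changes the quantity reported. If Levene's test passes, the reader gets a difference in means, which is what the sample size was planned to detect. If it fails, the reader gets medians and a rank comparison, even when the data pass the plan's own normality check. A preliminary test on the trial data thus decides which quantity represents the primary endpoint. At stake are some distortion of the rejection rate for a mean difference if arm sizes are unequal, and a little power.

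**Working it through.** **The plan's own figure.** The difference is 24 h and the SD 36 h, so d = 24/36 = 0.67. No power is stated; 80% is assumed here.

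- Normal approximation: n = 2(1.960 + 0.842)² / 0.667² = 35.3, so 36 per group.
- Noncentral t: 36.3, so 37 per group.
- Mann-Whitney, dividing the t-test n by its relative efficiency 3/π = 0.955: 36.31/0.955 = 38.02, so 39 per group and 78 in total. This matches the plan, but the plan does not say which test was used for sizing.
- With 39 per group, the t-test has 82.8% power (noncentral t).

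**Simulating the rule.** Inputs from the plan are 39 per group, alpha 0.05, means of 96 and 72 h, and the cut-off of 2.0 for skewness and kurtosis. Assumptions are Levene's test at 0.05 (the plan gives no level for it), the normality check applied to each arm, and all unequal SDs, splits and distribution shapes.

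*No treatment effect (identical distributions).* With normal, gamma and lognormal arms at SD 36 or 60 and splits of 39/39 and 50/28, the plan's rule rejected in 4.2% to 5.3% of trials and Welch in 3.8% to 5.4%.

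*Equal means, SD ratio 2 (30 vs 60), normal data:*

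| Split | Plan's rule | Welch when the normality check passes |
|---|---|---|
| 39/39 | 5.3% | 4.9% |
| 50/28, smaller arm more variable | 8.6% | 5.6% |
| Reverse, larger arm more variable | 3.6% | 4.9% |

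Separate runs of the 50/28 case gave 7.6% to 8.6% for the plan. Mann-Whitney at 39/39 gave up to 5.7% at an SD ratio of 2 and 5.0% to 5.1% at a ratio of 1.5. At a milder split of 45/33 and a ratio of 2, Mann-Whitney gave 6.8% with the smaller arm more variable and 4.5% in reverse, against 5.0% and 4.9% for Welch.

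*Power, 39/39, 96 vs 72 h:*

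| Data | Plan's rule | Welch when the normality check passes |
|---|---|---|
| Normal, SD 36 in both | 82% | 82% |
| Normal, SD 48 and 24 | 76% | 79% |
| Gamma, constant coefficient of variation 0.5 (SD 48 and 36) | 67% | 70% |

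In the last row the SDs differ only because the means do; Levene's test failed in about 35% of such trials. A real effect can therefore trigger the switch.

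**Change of quantity.** Take gamma data with mean 96 h in both arms and SDs of 36 and 72. The medians are 91.5 and 78.7 h. The two branches of the rule then describe different things.

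**The case against.** The strongest reply is that the rule does not break error control in the sense most readers mean. If treatment does nothing, the two distributions are the same, and the rule then rejects at about 5%. That stands.

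A reader might go further and infer that false positives reach 16% to 18%. Such figures can be produced with gamma data, a mean of 84 h in both arms and SDs of 30 and 60. They do not support that inference. The arms there differ in distribution: the medians are 80.5 and 70.2 h, and a patient in the wider arm resolves sooner with probability 0.56. Mann-Whitney is responding to a real difference in what it tests. Much of the excess also arrives through the non-normality route. Using Welch only where the normality check passes brings the figure down to about 12% to 13%, not to 5%. These are rejection rates under equal means but different distributions, and nothing in the plan suggests a twofold SD ratio.

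A reader might also infer from the bed numbers that the arms will be unequal. The Protocol section describes the swap of sides as the answer to that difference. Location-based assignment allows imbalance but does not imply it, and 50/28 has no source in the plan.

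Three further points stand. The distortion runs both ways, since with the larger arm more variable the rule is conservative. The move to medians is openly pre-specified, and a sample size of 39 is consistent with a rank test having been foreseen. Finally, Welch for every outcome would not be a free gain: for lognormal durations of 96 vs 72 h with coefficient of variation 0.7, it has about 45% power against 49% for the plan's rule.

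None of this makes Mann-Whitney a remedy for unequal variances when the data pass the normality check.

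**Conclusion.** The point holds in a narrow form and is minor. The plan answers a Levene failure with a test that does not address unequal variances, and in doing so moves away from the mean difference used for the sample size.

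At the planned 1:1 allocation with symmetric data the consequence is trivial: 5.3% to 5.7% against about 5%, at an assumed SD ratio of 2. With arms as unequal as 50/28, the equal-means rejection rate is about 8.5% or about 3.5%, depending on which arm is more variable, against about 5% for Welch. The power loss is about 3 points when SDs differ. Every one of these sizes rests on assumed SD ratios, splits and shapes.

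The documents do not support a claim that the rule inflates false positives when treatment has no effect, or that the use of Mann-Whitney for non-normal data is itself at fault. That is a separate choice.

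**What to change.** In Statistical methods, state that when the normality check passes, treatment groups will be compared with the Welch (unequal-variance) t-test whatever Levene's test shows, and that means and SDs will be reported. Levene's test can stay as a description but should no longer choose the test. Leave the Mann-Whitney route for non-normal data as it is.

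The cost is one sentence. It needs no extra patients or data and loses no power when the SDs are equal (82% either way at the planned effect).

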While each included patient’s data will be recorded retrospectively after randomization, we do believe that it is necessary to perform this study in a prospective manner rather than fully retrospective. It is not feasible to perform this study retrospectively as we would not be able to ensure adequate and equal numbers in each group within the medical critical care unit, especially considering how medical critical care patients are placed in other intensive care units within our institution based on bed availability. Unequal groups would unduly bias the results and make the analysis less meaningful in terms of contributing to the current body of evidence.

Any medication events, including adverse drug reactions or medication errors, will be routinely reported throughout the study to the UTMC Safety Intelligence system. Routine reports of events related to the study will be reviewed weekly by our medication safety office if necessary. Data will be collected continuously throughout the study duration and investigators will review the data for any concerning safety or efficacy differences between the treatment groups. Upon regular screening for adverse drug events, if any are detected, they will be not only be reported to the Safety Intelligence system but will also be reported for review by the IRB.

Per the FDA guidance for clinical investigators regarding the need for an investigational new drug (IND) application in human research studies, investigations are exempt if the drug is lawfully marketed in the U.S., the investigation is not intended to support a new indication or change the labeling of the drug, the investigation will not support a change in advertising for the drug, and the route of administration, dose, or any other factor of the investigation will not increase the risk associated with the drug⁷. Our study, since we are not changing standard of care and are using accepted, studied doses of hydrocortisone and fludrocortisone, meet these criteria for exemption from IND application.

Outcomes:

- Primary Endpoint:
 - Time to resolution of shock (defined as 24 hours vasopressor free)
- Secondary Endpoints:
 - ICU Length of Stay (LOS)
 - Hospital LOS
 - All-cause mortality at ICU discharge
 - All-cause mortality at hospital discharge
 - All-cause mortality at 28 days of admission
 - All-cause mortality at 90 days of admission
 - Withdrawal of treatment therapy during ICU stay

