 - Reinitiation of vasopressor therapy (after vasopressor free for 24 hours)
 - Reinitiation of hydrocortisone and/or fludrocortisone
 - Mechanical ventilator free days during ICU admission
 - Duration of steroid therapy
- Safety Endpoints
 - Documentation of two consecutive point of care blood glucose checks >180 mg/dl after initiation of hydrocortisone and/or hydrocortisone/fludrocortisone
 - Gastrointestinal bleed during study period (as documented by provider)
 - Severity of bleed as determined by GUSTO criteria
 - Severe: deadly bleeding; intracerebral bleeding or substantial hemodynamic compromise
 - Moderate: bleeding requiring transfusion
 - Mild: other bleeding not requiring transfusion or causing hemodynamic compromise
 - New initiation of renal replacement therapy during study period
 - Electrolyte abnormalities
 - Sodium level greater than 150 mEq/L during study period
 - Potassium level greater than 5.5 mEq/L during study period

Other Data Collected:

- Demographics: Age, sex, weight, height, BMI, ethnicity (race)
- Septic Shock Bundle initiated
- WBC at time of steroid initiation and at discontinuation

- Initial lactic acid level on admission
- Lactic acid level at initiation of vasopressors
- Vasopressor initiated (norepinephrine, epinephrine, phenylephrine, vasopressin, dopamine, dobutamine)
- Vasopressor dose when steroid therapy was initiated (mcg/min and mcg/kg/min)
- Max vasopressor dose during study period
- SOFA Score
- APACHE Score
- Charlson Comorbidity Index
- Site of infection (lung, intraabdominal, urogenital, skin, CNS, endocarditis, bacteremia, unknown, etc.)
- Non-contaminant, positive culture during study period with clinical correlation to septic shock event
 - Site of culture
 - Gram Positive
 - Gram Negative
 - Viral
 - Fungal
 - Organism
- Comorbidities:
 - Documented heart failure
 - Documented chronic kidney disease stage III-IV not requiring renal replacement therapy at baseline
- Documentation of concurrent cardiogenic shock during study period
- Serum creatinine at initiation of steroid therapy
- Serum creatinine at discontinuation of steroid therapy
- Renal replacement therapy at the initiation of steroid therapy
- Mechanical ventilation at initiation of steroid therapy
- Other systemic steroid use (methylprednisolone, dexamethasone, prednisone) prior to pressor initiation
- Systemic steroid use prior to admission (home medication)

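### All binary outcomes, including four mortality endpoints and new renal replacement therapy, get only an unadjusted chi-square and a crude relative risk, although prognostic variables are collected and arms are formed by unit side and period

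*Combined protocol and SAP*

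**What the plan says.** The Statistical methods section gives categorical outcomes frequencies, percentages and one test: "Chi-square tests will be used to test for significant associations between the treatment groups and categorical outcomes". It adds: "Relative risk with 95% confidence intervals will be reported for significant categorical associations". The only regression is for the primary endpoint: "Multiple regression analysis will be performed with time to resolution of shock as the outcome". Its covariates are not named. No logistic, stratified or other adjusted analysis is planned for any binary endpoint. The heart failure and kidney disease subanalysis looks at subsets and is not adjustment.

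The binary endpoints under Outcomes include "All-cause mortality at ICU discharge", "All-cause mortality at hospital discharge", "All-cause mortality at 28 days of admission" and the same at 90 days. New renal replacement therapy is a safety endpoint.

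Other Data Collected lists SOFA and APACHE, with no scoring time, and "Serum creatinine at initiation of steroid therapy". It also lists whether the patient was on renal replacement therapy when steroids began.

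On allocation, the Protocol section says: "Steroid therapy assignments will be randomized based on patient location". One side of the unit gives hydrocortisone alone and the other gives the combination for three months. The sides then swap. The stated reasons are the unequal bed numbers and possible acuity differences between sides. Starting hydrocortisone, and so entering the study, is left to the provider, and treatment is open-label.

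**The concern.** Individual randomisation makes any baseline difference between arms a matter of chance, which the chi-square's error rate already allows for. Here the unit of assignment is a side of the unit in a three-month period: two sides, two periods, four cells. The provider who decides whether to start hydrocortisone can know which regimen that side is using. A systematic difference in severity between arms is therefore possible, and a raw 2x2 comparison cannot allow for one. Such a difference would be read as an effect of fludrocortisone on death or renal failure, or would hide one.

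Even with balanced arms, leaving out a prognostic covariate gives up some precision. The protocol's Background treats baseline severity as a reason why earlier trials disagreed on mortality, yet the mortality comparison makes no use of it. With no adjusted model pre-specified, any later adjustment would use covariates chosen after the results were known.

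**Working it through.** **The plan's own figure.** No sample size or power is given for a binary outcome. The 39 per group is for the primary endpoint: d = 24/36 = 0.667, two-sided alpha 0.05, power not stated. At an assumed 80% power the t-test needs 36.3, so 37 per group. Dividing by 0.955, the Mann-Whitney relative efficiency, gives 38.02, so 39. The figure is reproducible, and 39 per arm is used below.

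**What the swap removes.** Let side 2 minus side 1 in mean severity be D1 in the first period and D2 in the second. The combination arm is side 2 in the first period and side 1 in the second. With equal numbers in the four cells, the gap between arms is (D1 − D2)/2. A constant difference (D1 = D2) cancels. A 1.4-point gap between arms would need the side difference to change by 2 × 1.4 = 2.8 points between periods. Selection arising from knowledge of the assigned regimen follows the regimen when the sides swap, so it is not cancelled.

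**Assumptions (not in the documents).** Control mortality is 40%, so about 0.40 × 78 = 31 deaths if the arms do not differ. Three settings for SOFA, as odds ratio per point and SD: A 1.2 and 3; B 1.25 and 3.5; C 1.3 and 4. The score is normal and mortality is logistic in the score.

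**Chance gaps.** The standard error of the difference in mean SOFA is SD × √(2/39) = 0.679, 0.793 and 0.906. The probability of a gap above g in either direction is 2 × (1 − Φ(g/SE)):
- above 1 point: 14%, 21%, 27%
- above 1.4 points: 4%, 8%, 12%

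**Simulation.** 20,000 replicates per cell. Each entry is the rejection rate of the Pearson chi-square, then of the likelihood-ratio test for arm in a logistic model with the score. The simulation standard error is about 0.2 points at a 10% rate, √(0.1 × 0.9/20,000), and 0.3 at 72%.

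| Scenario | A | B | C |
|---|---|---|---|
| No effect, chance imbalance only | 5.2% / 5.3% | 5.1% / 5.5% | 5.1% / 5.6% |
| No effect, systematic 1.4-point gap | 8.6% / 5.5% | 9.6% / 5.5% | 10.1% / 5.4% |
| 40% v 30%, no systematic gap | 15.3% / 16.6% | 15.7% / 17.6% | 15.5% / 18.4% |
| 40% v 15%, no systematic gap | 72.1% / 74.0% | 72.6% / 76.8% | 72.1% / 79.0% |

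With the systematic gap and no treatment effect, expected mortality in the sicker arm is 45.8%, 46.8% and 47.4%, against 40%. The power gains are 1.4, 2.0 and 3.0 points at 40% v 30%, and 2.0, 4.2 and 6.9 points at 40% v 15%. The likelihood-ratio test runs slightly above the chi-square under the null, which accounts for a few tenths of a point. Runs of 2,500 to 4,000 replicates in the same settings scatter around these values: 8% to 11% for the error, 1 to 2 points and 2 to 8 points for the gains.

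**Sensitivity.** With 45% mortality and a score whose AUC is 0.68 to 0.80, a systematic gap of 0.3 SD gives a chi-square error of 8% to 10%, and 0.5 SD gives 12% to 20%. The adjusted test stays at 5% to 6%. With 50% control mortality and absolute reductions of 18 to 26 points, the power gain is 4 to 13 points.

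No calculation was made for renal replacement therapy, because the documents give neither its rate nor the prognostic strength of creatinine.

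**The case against.** Unadjusted tests for secondary and safety endpoints in a 78-patient single-centre study, with regression kept for the primary endpoint, are a defensible choice. That stands: this is an improvement, not the correction of an error.

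Three stronger readings are tempting, and the documents support none of them.
- A reader might infer that the frequent chance gaps inflate the false-positive rate. They do not. With chance imbalance only, the chi-square holds about 5%.
- A reader might take 1.4 SOFA points as the gap to expect between these arms. It is the contrast of 12 and 10.6 that the Background quotes from two different published trials. It says nothing about MCC1 and MCC2, and the swap cancels any stable difference between sides. The 9% to 10% error is therefore conditional on a systematic gap whose size the documents do not indicate.
- A reader might take the power gain as large. It is small at 40% versus 30%, where power is only 15% to 18% with or without adjustment.

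It is also fair to say that SOFA and APACHE are not documented as baseline values, because their scoring time is not stated. Only creatinine is tied to steroid start. Finally, one severity score does not deal with clustering by side and period. These limits shape the fix. None of them is a reason to leave pre-steroid prognostic data out of the mortality and renal comparisons.

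**Conclusion.** The point holds as a recommended improvement to the secondary and safety analyses. The plan compares every binary endpoint without adjustment. The allocation leaves room for a systematic severity difference that the swap only partly controls, and suitable covariates are on the collection list once the scoring time is fixed.

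Under the assumed 40% mortality, 39 per arm, SOFA SD 3 to 4 and odds ratio 1.2 to 1.3 per point:
- Adjustment leaves the error near 5% whether or not a gap exists. The chi-square reaches about 9% to 10% if a systematic 1.4-point gap exists.
- Adjustment adds about 1 to 3 points of power at 40% versus 30%, and 2 to 7 at 40% versus 15%.

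These figures are illustrative. The documents do not show that the arms will differ in severity, that the chi-square is invalid, or that the stated sample size is wrong.

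**What to change.** In Statistical methods:
- For each mortality endpoint, pre-specify a logistic regression on arm plus one severity score, SOFA or APACHE, named in advance and scored from values before the first hydrocortisone dose. Add unit side or period if events allow. With about 31 deaths under the 40% assumption, one or two covariates is the limit.
- For new renal replacement therapy, restrict the analysis to patients not on it at steroid start and adjust for creatinine at that time. Use a penalised fit if events are few.
- Report the standardised risk difference and relative risk with 95% CI whether or not significant, and keep the chi-square as a supporting result.
- State how a missing score is handled, for example by simple imputation.

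The cost is a few sentences, a handful of extra models, and a defined scoring time under Other Data Collected, which may mean some re-abstraction of records. No extra patients are needed. Adjustment does not resolve clustering by side and period, which should be listed as a remaining limitation.

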- Continuation of baseline/prior steroid in combination with hydrocortisone/fludrocortisone
- Inhaled corticosteroid use
- Intubation with etomidate
- Amount of diuretics received during study period
- Acute respiratory distress syndrome documented during study period
- Administration of neuromuscular blocker during study period

Statistical Analysis:

Statistical Power

In order to achieve adequate statistical power for the proposed prospective trial, an a priori sample size calculation was completed based on an evidence-based measure of effect size from the APROCCHSS and CORTICUS trials^{3,4}. The evidence-based difference between the treatment groups was 24 hours (Group 1 $M = 96$, $SD = 36$; Group 2 $M = 72$, $SD = 36$), leading to a Cohen's d effect size of 0.67. With a two-tailed hypothesis, an effect size of $d = 0.67$, an alpha value of 0.05, and equal allocation to treatment groups (1:1), 39 participants would be needed for each treatment group. This means the total sample size will be $n = 78$ in order to achieve adequate statistical power for the trial.

Statistical methods

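### Relative risks with confidence intervals are planned only for significant categorical results, so a non-significant mortality or safety comparison has no planned between-arm estimate

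*Combined protocol and SAP*

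**What the plan says.** The section Statistical methods handles categorical outcomes in three sentences.

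- Description: "Frequency and percentage statistics will be used to analyze categorical demographic, predictor, confounding, and outcome variables of interest for the sample".
- Test: "Chi-square tests will be used to test for significant associations between the treatment groups and categorical outcomes". The significance level for all analyses is 0.05.
- Effect estimate: "Relative risk with 95% confidence intervals will be reported for significant categorical associations".

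No other part of the document plans a risk difference, odds ratio, hazard ratio or unconditional interval for a binary outcome. The regression coefficients and their standard errors are not tied to significance, but that model covers only time to resolution of shock.

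The Outcomes section lists 12 binary outcomes that fall under the rule:

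- Seven secondary: death by ICU discharge, by hospital discharge, at 28 days ("All-cause mortality at 28 days of admission") and at 90 days; withdrawal of treatment; restart of vasopressors; restart of steroids.
- Five safety: raised glucose, gastrointestinal bleed, new renal replacement therapy, high sodium, high potassium.

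The four mortality outcomes overlap, so these are not 12 independent pieces of information.

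**The concern.** The rule lets the p-value decide which effect sizes are shown. This has two consequences.

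First, a non-significant comparison comes with no interval. In a trial sized only for the primary endpoint, a non-significant mortality or safety result may be read as no difference, when the interval would show that a sizeable difference in either direction is still compatible with the data.

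Second, with small arms only a large observed RR can pass the test. The RRs that pass overstate the true effect on average, and the smaller ones that would give context are left out.

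The background section presents mortality as the unresolved question about these drugs, so the outcomes affected are ones readers will look for.

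**Working it through.** **Sample size.** The Statistical Power section gives means of 96 and 72 hours, SD 36 and two-sided alpha 0.05, and concludes that "39 participants would be needed for each treatment group". It states no power. At an assumed 80%, the exact two-sample t-test needs 36.3, so 37 per arm. Dividing by the Mann-Whitney efficiency gives 36.3 / 0.955 = 38.0, which rounds up to 39. At 39 per arm the t-test has 82.8% power. The figure is therefore reproducible to within rounding and choice of test. It concerns the primary endpoint only and is used here just as n.

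**Assumptions.** The documents give no event rates, so all risks and counts below are assumed. The test is the uncorrected Pearson chi-square, because the plan names no variant.

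**Chance that an RR would be reported.** For true risks p1 and p2, sum Bin(a; 39, p1) × Bin(b; 39, p2) over all pairs (a, b) with p < 0.05. The medians are taken over the same pairs.

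| True risks | True RR | Chance RR is reported | Median RR, significant trials | Median RR, all trials |
|---|---|---|---|---|
| 20% vs 10% | 2.0 | 24% | 4.5 | 2.0 |
| 50% vs 40% | 1.25 | 15% | 1.83 | 1.25 |
| 60% vs 40% | 1.5 | 44% | 1.82 | 1.5 |
| 70% vs 40% | 1.75 | 78% | 1.87 | 1.75 |

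Modest differences seldom get an interval; large ones usually do. The gap between the last two columns is the selection effect. It is marked when the chance of significance is low and small when it is high.

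**Results with no planned interval.** Formulas, with a and b events out of 39:

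- X² = 78 × [a(39 − b) − b(39 − a)]² / [39 × 39 × (a + b) × (78 − a − b)]
- SE(log RR) = √(1/a − 1/39 + 1/b − 1/39); 95% CI = RR × exp(±1.96 SE)

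24 versus 16 deaths:

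- X² = 78 × (24 × 23 − 16 × 15)² / (39 × 39 × 40 × 38) = 78 × 312² / 2,311,920 = 3.28, so p = 0.070.
- RR = 1.5, SE = 0.230, CI 0.96 to 2.35.
- Risk difference 8/39 = 21 percentage points; Newcombe interval −2 to 40.

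10 versus 4 events:

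- X² = 78 × (10 × 35 − 4 × 29)² / (39 × 39 × 14 × 64) = 78 × 234² / 1,362,816 = 3.13, so p = 0.077.
- RR = 2.5, SE = 0.547, CI 0.86 to 7.30.
- Risk difference 6/39 = 15 percentage points; Newcombe interval −2 to 32.

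**How sharp the cut is.** With 16 of 39 events in one arm, every count from 9 to 24 in the other is non-significant (RR 0.56 to 1.50) and carries no planned interval. At 25 versus 16, X² = 78 × 351² / (39 × 39 × 41 × 37) = 4.16 and p = 0.041, so the RR of 1.56 would be reported. One event decides whether the reader is given an estimate.

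**The case against.** The strongest reply is that little information is lost. Frequencies and percentages are planned whatever the p-value, and for an unadjusted two-by-two table the counts by arm fix the crude RR and its interval. This stands, and it is why the weight is minor. It is not a full answer: the descriptive sentence speaks of the sample and does not promise results by arm, and a reader's own calculation is not a planned estimate.

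A second reply is that the sentence commits to RRs for significant results and does not forbid them elsewhere. That is also fair. The document supports saying that no estimate is planned for a non-significant result, not that one is prohibited. A reader might infer that non-significant results would be hidden altogether; the planned frequencies and percentages contradict that.

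A reader might also infer that the rule breaks down even when triggered, because 4 versus 0 events is significant (p = 0.040) but has no finite RR. That depends on the uncorrected chi-square with only two expected events per arm; Fisher's exact test gives p = 0.115. The plan does not name the variant, so the argument belongs to the choice of small-count test and is not relied on here.

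Allocation by unit side and three-month block ("Steroid therapy assignments will be randomized based on patient location") raises the question of whether intervals that treat patients as independent are too narrow. That is a separate issue. So is the lack of a planned between-arm difference for continuous secondary outcomes such as length of stay, which does not depend on significance. Bleed severity has three levels, which a single RR cannot summarise, so it too lies outside this point.

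**Conclusion.** The concern holds, with minor weight. The plan states a rule that ties the RR and its interval to a significant test, and nothing elsewhere supplies an unconditional estimate for the four mortality outcomes, the other binary secondary outcomes or the binary safety outcomes.

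The size depends on assumed event rates, 39 per arm and an uncorrected chi-square. Fisher's exact test would make the trigger stricter. The stronger reading, that RRs would hardly ever be shown, is not supported: at 70% versus 40% one would be reported about 78% of the time. Nor does the rule undermine the trial's main result, since the primary analysis, the data collected and the tests are untouched. Reporting every RR would not add power or shrink the significant ones; it would remove the selection and show what each non-significant comparison leaves open.

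**What to change.** Replace the relative-risk sentence under Statistical methods with:

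> For every binary secondary and safety outcome, the number and percentage in each arm and the relative risk with its 95% confidence interval will be reported whatever the p-value, together with the risk difference and its 95% confidence interval; where an arm has no events, the counts and risk difference will be reported.

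The choice of interval method can be left to the trial statistician. If it is not available in the named SPSS version, a closed-form interval such as Newcombe's can be computed in a spreadsheet, with a few words added to the software sentence.

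The cost is a short text edit. No new data are needed, and the primary endpoint, sample size and patient procedures do not change. The only downside is that wide intervals are shown.
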